11.4. Management of Severe Hypersensitivity Reaction and Flu-Like Symptoms

As with all monoclonal antibody therapies, avelumab can induce flu-like symptoms and hypersensitivity reactions, including impaired airway, decreased oxygen saturation (<92%), confusion, lethargy, hypotension, pale/clammy skin, and cyanosis.

Avelumab should be administered in a setting that allows for immediate access to an intensive care unit or equivalent environment and administration of therapy for anaphylaxis, such as the ability to implement immediate resuscitation measures. Steroids (dexamethasone 10 mg), epinephrine (1:1,000 dilution), allergy medications (IV antihistamines), bronchodilators, or equivalents, and oxygen should be available for immediate access. Subjects should be instructed to report any delayed reactions to the Investigator immediately.

For prophylaxis of flu-like symptoms, 25 mg indomethacin or comparable non-steroidal anti-inflammatory drug (NSAID) dose (e.g. ibuprofen 600 mg, naproxen sodium 500 mg) may be administered 2 hours before and 8 hours after the start of each dose of avelumab IV infusion. Alternative treatments for fever (e.g. paracetamol or ibuprofen) may be given to patients at the discretion of the investigator.

11.5. Management of Tumor Lysis Syndrome

Because avelumab can induce antibody-dependent cell-mediated cytotoxicity (ADCC), there is a potential risk of tumor lysis syndrome (TLS). Should this occur, patients should be treated according to local guidelines and the management algorithm (Appendix 6) published by Howard et al.⁴⁷

11.6. Management of Immune-Related Adverse Events (irAEs)

Since inhibition of PD-L1 stimulates the immune system, immune-related adverse events (irAEs) may occur. **Any adverse event judged by the investigator to be possibly, probably or definitely immune-related should be managed according to the guidance in this section for the management of immune-related adverse events, except for circumstances in which local or other standards known to exist are felt by the investigator to present a more medically appropriate course of management.**

Treatment of irAEs is mainly dependent upon severity (NCI-CTCAE grade):

- Grade 1 to 2: treat symptomatically or with moderate dose steroids, more frequent monitoring
- Grade 1 to 2 (persistent): manage similar to high grade AE (Grade 3 to 4)
- Grade 3 to 4: treat with high dose corticosteroids

Some potential irAEs described with anti-PD-L1 drugs such as avelumab may be similar to toxicities related to disease (e.g. diarrhea related to adenocarcinoma of the small intestine). In general: Rule out non-inflammatory causes; if non-inflammatory cause is identified, treat accordingly and continue study treatment according to protocol.

Corticosteroids are a primary therapy for immuno-oncology drug-related adverse events. Patients treated for irAEs with IV steroids may be switched to an equivalent dose of oral corticosteroids (e.g. prednisone) at start of tapering or earlier, once sustained clinical improvement is observed. Lower bioavailability of oral corticosteroids should be taken into account when switching to the equivalent dose of oral corticosteroids.

MANAGEMENT of GASTROINTESTINAL IMMUNE-RELATED ADVERSE EVENTS (irAEs)		
Diarrhea / Colitis	Management	Follow-Up

Grade 1
 
Diarrhea: < 4 stools/day over baseline
 
Colitis: Asymptomatic
	
 • Continue avelumab therapy per protocol. • Symptomatic treatment (e.g. loperamide). 	
 • Close monitoring for worsening symptoms. • Educate patient to immediately report worsening. 
If worsens:
 
 • Treat as Grade 2, or Grade 3 to 4.

MANAGEMENT of GASTROINTESTINAL IMMUNE-RELATED ADVERSE EVENTS (irAEs)		
Diarrhea / Colitis	Management	Follow-Up

Grade 2
 
Diarrhea: 4 to 6 stools per day over baseline; IV fluids indicated < 24 hours; not interfering with ADL
 
Colitis: Abdominal pain; blood in stool
	
 • Delay avelumab therapy per protocol. • Symptomatic treatment. 	
If improves to Grade ≤1:
 
 • Resume avelumab therapy per protocol. 
If persists > 5-7 days or recurs:
 
 • treat as Grade 3 or 4.

Grade 3 to 4
 
Diarrhea (Grade 3): ≥ 7 stools per day over baseline; incontinence; IV fluids ≥ 24 hrs; interfering with ADL
 
Colitis (Grade 3): Severe abdominal pain, medical intervention indicated, peritoneal signs
 
Grade 4: Life-threatening, perforation
	
 • Withhold avelumab for Grade 3 • Permanently discontinue avelumab for Grade 4 or recurrent Grade 3 • 1.0 to 2.0 mg/kg/day methylprednisolone IV or equivalent. • Add prophylactic antibiotics for opportunistic infections. • Consider lower endoscopy. 	
If improves:
 
 • Continue steroids until Grade ≤ 1, then taper over at least 1 month; resume avelumab therapy following steroids taper (for initial Grade 3) 
If worsens, persists > 3 to 5 days, or recurs after improvement:
 
 • Add infliximab 5 mg/kg (if no contraindication). Note: Infliximab should not be used in cases of perforation or sepsis.

Opiates/narcotics may mask symptoms of perforation. Infliximab should not be used in cases of perforation or sepsis.

MANAGEMENT of DERMATOLOGIC IMMUNE-RELATED ADVERSE EVENTS (irAEs)		
Rash	Management	Follow-Up

Grade 1 to 2 Covering ≤ 30% body surface area (BSA)
	
 Continue avelumab therapy per protocol. Symptomatic therapy (for example, antihistamines, topical steroids) 	
If persists > 1 to 2 weeks or recurs:
 
 withhold avelumab therapy Consider skin biopsy. 
 Consider 0.5 to 1.0 mg/kg/day methylprednisolone IV or oral equivalent. Once improving, taper steroids over at least 1 month, consider prophylactic antibiotics for opportunistic infections, and resume avelumab therapy following steroids taper. 
If worsens:
 
 Treat as Grade 3 to 4.

Grade 3 Covering > 30% BSA;
 
Grade 4 life threatening consequences
	
 Withhold avelumab for Grade 3 Permanently discontinue for Grade 4 or recurrent Grade 3. Consider skin biopsy. Dermatology consult. 1.0 to 2.0 mg/kg/day methylprednisolone IV or IV equivalent. Add prophylactic antibiotics for opportunistic infections. 	
If improves to Grade ≤ 1:
 
 Taper steroids over at least 1 month and add prophylactic antibiotics for opportunistic infections Resume avelumab therapy following steroids taper (for initial Grade 3).

MANAGEMENT of PULMONARY IMMUNE-RELATED ADVERSE EVENTS (irAEs)		
Pneumonitis	Management	Follow-Up

Grade 1 Radiographic changes only
	
 Consider withholding avelumab therapy. Monitor for symptoms every 2 to 3 days. Consider Pulmonary and Infectious Disease consults. 	
 Re-assess at least every 3 weeks. 
If worsens:
 
 Treat as Grade 2 or Grade 3 to 4.

Grade 2 Mild to moderate new symptoms
	
 Withhold avelumab therapy Pulmonary and Infectious Disease consults. Monitor symptoms daily, consider hospitalization. 1.0 to 2.0 mg/kg/day methylprednisolone IV or IV equivalent. Add prophylactic antibiotics for opportunistic infections Consider bronchoscopy, lung biopsy. 	
 Re-assess every 1 to 3 days. 
If improves:
 
 When symptoms return to Grade \leq 1, taper steroids over at least 1 month and then resume avelumab therapy per protocol following steroids taper and consider prophylactic antibiotics. 
If not improving after 2 weeks or worsening:
 
 Treat as Grade 3 to 4.

Grade 3 to 4 Grade 3: Severe new symptoms; New / worsening hypoxia; Grade 4: life-threatening
	
 Permanently discontinue avelumab therapy per protocol. Hospitalize. Pulmonary and Infectious Disease consults. 1.0 to 2.0 mg/kg/day methylprednisolone IV or IV equivalent. Add prophylactic antibiotics for opportunistic infections. Consider bronchoscopy, lung biopsy. 	
If improves to Grade \leq 1:
 
 Taper steroids over at least 1 month. 
If not improving after 48 hours or worsening:
 
 Add additional immunosuppression (e.g. infliximab, cyclophosphamide, intravenous immunoglobulin, or mycophenolate mofetil).

Evaluate with imaging and pulmonary consultation as appropriate.

MANAGEMENT of HEPATIC IMMUNE-RELATED ADVERSE EVENTS (irAEs)		
Elevated Liver Function Test (LFT)	Management	Follow-Up

Grade 1
 
AST or ALT > ULN to 3.0 x ULN and/or total bilirubin > ULN to 1.5 x ULN
	
 Continue avelumab therapy per protocol. 	
 Continue liver function monitoring per protocol. 
If worsens:
 
 Treat as Grade 2 or Grade 3 to 4.

Grade 2
 
AST or ALT > 3.0 to ≤ 5 x ULN and/or total bilirubin > 1.5 to ≤ 3 x ULN
	
 Delay avelumab therapy per protocol. Increase frequency of monitoring to every 3 days. 	
If returns to Grade ≤ 1:
 
 Resume routine monitoring, resume avelumab therapy per protocol. 
If elevations persist > 5 to 7 days or worsen:
 
 Treat as Grade 3 or 4.

Grade 3-4
 
AST or ALT > 5 x ULN and/or total bilirubin > 3 x ULN
	
 Permanently discontinue avelumab therapy. Increase frequency of monitoring to every 1 to 2 days. 1.0 to 2.0 mg/kg/day methylprednisolone IV or IV equivalent. Add prophylactic antibiotics for opportunistic infections. Consult gastroenterologist/hepatologist Consider obtaining MRI/CT scan of liver and liver biopsy if clinically warranted. 	
If returns to Grade ≤ 1:
 
 Taper steroids over at least 1 month. 
If does not improve in > 3 to 5 days, worsens or rebounds:
 
 Add mycophenolate mofetil 1 gram (g) twice daily (BID). If no response within an additional 3 to 5 days, consider other immunosuppressants per local guidelines.
MANAGEMENT of RENAL IMMUNE-RELATED ADVERSE EVENTS (Renal irAEs)		
Renal Disorder	Management	Follow-Up

Grade 1
 
Creatinine increased > ULN to 1.5 x ULN
	
Continue avelumab therapy
	
Continue renal function monitoring
 
If worsens:
 
Treat as Grade 2 to 3 or 4.

Grade 2 to 3 Creatinine increased > 1.5 and ≤ 6 x ULN
	
Withhold avelumab therapy Increase frequency of monitoring to every 3 days 1.0 to 2.0 mg/kg/day prednisone or equivalent. Add prophylactic antibiotics for opportunistic infections Consider renal biopsy
	
If returns to Grade ≤1: Taper steroids over at least 1 month, and resume avelumab therapy following steroids taper. If worsens: Treat as Grade 4.

Grade 4 Creatinine increased > 6 x ULN
	
Permanently discontinue avelumab therapy Monitor creatinine daily 1.0 to 2.0 mg/kg/day prednisone or equivalent. Add prophylactic antibiotics for opportunistic infections Consider renal biopsy Nephrology consult
	
If returns to Grade ≤1: Taper steroids over at least 1 month.

MANAGEMENT of ENDOCRINE IMMUNE-RELATED ADVERSE EVENTS (irAEs):		
Endocrine Disorder	Management	Follow-Up

Grade 1 or 2 endocrinopathies (hypothyroidism, hyperthyroidism, adrenal insufficiency, type I diabetes mellitus)
	
 • Continue avelumab therapy per protocol. • Endocrinology consult if needed 
 • Start thyroid hormone replacement therapy for hypothyroidism), anti-thyroid treatment (for hyperthyroidism), corticosteroids (for adrenal insufficiency) or insulin (for Type I diabetes mellitus) as appropriate. • Rule out secondary endocrinopathies (i.e. hypopituitarism/hypophysitis) 	
 • Continue hormone replacement/suppression and monitoring of endocrine functions as appropriate.

Grade 3 or Grade 4 Endocrinopathies (hypothyroidism, hyperthyroidism, adrenal insufficiency, Type I diabetes mellitus)
	
 • Withhold avelumab therapy • Consider hospitalization • Endocrinology consult • Start thyroid hormone replacement therapy (for hypothyroidism), anti-thyroid treatment (for hyperthyroidism), corticosteroids (for adrenal insufficiency), or insulin (for Type I diabetes mellitus) as appropriate • Rule-out secondary endocrinopathies (i.e. hypopituitarism / hypophysitis) 	
 • Resume avelumab once symptoms and/or laboratory tests improve to Grade ≤ 1 (with or without hormone replacement/suppression). • Continue hormone replacement/suppression and monitoring of endocrine function as appropriate.

Hypopituitarism/Hypophysitis (secondary endocrinopathies)
	
 • If secondary thyroid and/or adrenal insufficiency is confirmed (i.e. subnormal serum FT4 with inappropriately low TSH and/or low serum cortisol with inappropriately low ACTH): • Refer to endocrinologist for dynamic testing as indicated and measurement of other hormones (FSH, LH, GH/IGF -1, PRL, testosterone in men, estrogens in women) • Hormone replacement/suppressive therapy as appropriate • Perform pituitary MRI and visual field examination as indicated 
If hypophysitis confirmed:
 
 • Continue avelumab if mild symptoms with normal MRI • Repeat MRI in one month • Withhold avelumab if mild symptoms of hypophysitis and/or abnormal MRI • Consider hospitalization • Initiate corticosteroids (1 to 2 mg/kg/day prednisone or equivalent) followed by corticosteroids taper during at least 1 month • Add prophylactic antibiotics for opportunistic infections 	
 • Resume avelumab once symptoms and hormone tests improve to Grade ≤ 1 (with or without hormone replacement). • In addition for hypophysitis with abnormal MRI, resume avelumab only once shrinkage of the pituitary gland on MRI/CT scan is documented. • Continue hormone replacement therapy suppression as appropriate.

MANAGEMENT OF CARDIAC IMMUNE-RELATED ADVERSE EVENTS (irAEs)		
Myocarditis	Management	Follow-up
New onset of cardiac signs or symptoms and / or new laboratory cardiac biomarker elevations (e.g. troponin, CK-MB, BNP) or cardiac imaging abnormalities suggestive of myocarditis.	
 • Withhold avelumab therapy. • Hospitalize. • In the presence of life threatening cardiac decompensation, consider transfer to a facility experienced in advanced heart failure and arrhythmia management. • Cardiology consult to establish etiology and rule-out immune-mediated myocarditis. • Guideline based supportive treatment as per cardiology consult.* • Consider myocardial biopsy if recommended per cardiology consult. 	
 • If symptoms improve and immune-mediated etiology is ruled out, re-start avelumab therapy. • If symptoms do not improve/worsen, viral myocarditis is excluded, and immune-mediated etiology is suspected or confirmed following cardiology consult, manage as immune-mediated myocarditis.
Immune-mediated myocarditis	
 • Permanently discontinue avelumab. • Guideline based supportive treatment as appropriate as per cardiology consult.* • Methylprednisolone 1 to 2 mg/kg/day 	
 • Once improving, taper steroids over at least 1 month • Prophylactic antibiotics for opportunistic infections. • If no improvement or worsening, consider additional immunosuppressants (e.g. azathioprine, cyclosporine A)

*Local guidelines, or eg. ESC or AHA guidelines ESC guidelines website: https://www.escardio.org/Guidelines/Clinical-Practice-Guidelines AHA guidelines website: http://professional.heart.org/professional/GuidelinesStatements/searchresults.jsp?q=&y=&t=1001
		

MANAGEMENT OF OTHER irAEs (not described above)		
Grade of other irAEs (NCI-CTCAE v4)	Management	Management

Grade 2 or Grade 3 clinical signs or symptoms suggestive of a potential irAE	
 • Withhold avelumab therapy pending clinical investigation 	
 • If irAE is ruled out, manage as appropriate according to the diagnosis and consider re-starting avelumab therapy • If irAE is confirmed, treat as Grade 2 or 3 irAE.
Grade 2 irAE or first occurrence of Grade 3 irAE	
 • Withhold avelumab therapy • 1.0 to 2.0 mg/kg/day prednisone or equivalent • Add prophylactic antibiotics for opportunistic infections • Specialty consult as appropriate 	
 • If improves to Grade \leq 1: • Taper steroids over at least 1 month and resume avelumab therapy following steroids taper.
Recurrence of same Grade 3 irAEs	
 • Permanently discontinue avelumab therapy • 1.0 to 2.0 mg/kg/day prednisone or equivalent • Add prophylactic antibiotics for opportunistic infections • Specialty consult as appropriate 	
 • If improves to Grade \leq 1: • Taper steroids over at least 1 month.
Grade 4	
 • Permanently discontinue avelumab therapy • 1.0 to 2.0 mg/kg/day prednisone or equivalent and/or other immunosuppressant as needed • Add prophylactic antibiotics for opportunistic infections • Specialty consult. 	
 • If improves to Grade \leq 1: • Taper steroids over at least 1 month
Requirement for 10 mg per day or greater prednisone or equivalent for more than 12 weeks for reasons other than hormonal replacement for adrenal insufficiency Persistent Grade 2 or 3 irAE lasting 12 weeks or longer	
 • Permanently discontinue avelumab therapy • Specialty consult 	

Abbreviations: ACTH=adrenocorticotrophic hormone; ADL=activities of daily living; ALT=alanine aminotransferase; AST=aspartate aminotransferase; BNP=B-type natriuretic peptide; CK-MB=creatinine kinase MB; CT= computed tomography; FSH=follicle-stimulating hormone; GH=growth hormone; IGF-1=insulin-like growth factor 1; irAE=immune related adverse event; IV=intravenous; LH=luteinizing hormone; MRI=magnetic resonance imaging; NCI CTCAE=National Cancer Institute Common Terminology Criteria for Adverse Events; PRL=prolactin; T4=thyroxine; TSH=thyroid stimulating hormone; ULN=upper limit of normal.

12. DRUG FORMULATION, SUPPLY AND STORAGE

12.1. Description of Avelumab

The active pharmaceutical ingredient in avelumab drug product is a fully human antibody (calculated molecular weight of 143,832 Daltons) of the immunoglobulin G (IgG) 1 isotype that specifically targets and blocks PD-L1, the ligand for PD-1.

Avelumab drug product is a sterile, clear, and colorless concentrate for solution intended for intravenous (i.v.) administration.

12.2. Packaging and Labeling of Avelumab

Avelumab will be provided by EMD Serono. Avelumab drug product is a sterile solution intended for intravenous (i.v.) administration.

Avelumab drug product is a sterile, clear, and colorless concentrate for solution typically presented at concentrations of 10 mg/mL and 20 mg/mL in single use glass vials closed with a rubber stopper and sealed with an aluminum Flip Off® crimp seal closure.

Each single-use 10 mg/mL vial typically contains 80 mg of avelumab as a preservative-free acetate-buffered solution (pH 5.5) containing Mannitol, Methionine, and Polysorbate 20 (Tween 20).

Each single-use 20 mg/mL vial typically contains 200 mg of avelumab as a preservative-free acetate-buffered solution (pH 5.2) containing Mannitol and Polysorbate 20 (Tween 20).

For avelumab drug product, only excipients that conform to the current European Pharmacopeia (Ph. Eur.) and/or the current United States Pharmacopeia (USP) are used.

12.3. Storage of Avelumab

Avelumab drug product must be stored at 2°C to 8°C until use, and it must not be frozen.

Avelumab drug product stored at room (23°C to 27°C) or higher temperatures for extended periods of time might be subject to degradation. Rough shaking of the solution must be avoided.

For application in clinical trials, avelumab drug product must be diluted with 0.45% or 0.9% saline solution (sodium chloride injection) supplied in an infusion bag.

It is recommended that diluted avelumab solution be used immediately. The chemical and physical in-use stability for the infusion solution of avelumab in 0.45% or 0.9% saline solution has been demonstrated for a total of 24 hours at room temperature. However, from a microbiological point of view, the diluted solution should be used immediately and is not intended to be stored unless dilution has taken place in controlled and validated aseptic conditions. If not used immediately, in-use storage times and conditions prior to administration are the responsibility of the user.

No other drugs should be added to the solution for infusion containing avelumab.

12.4. Accountability of Avelumab

Discarded volumes of avelumab should be disposed of as clinical waste. Partially full and empty vials may be destroyed at the site by the appropriate site personnel (e.g. Pharmacist or Study Nurse/Coordinator) following local environmental requirements and institutional policies. All

destruction must be fully documented on an Investigational Product Accountability Log (IPAL) or similar at the time of destruction.

13. MEASUREMENT of EFFECT

13.1. Definitions

For purposes of this study, patients should be re-evaluated for response every 8 weeks. Response and progression will be evaluated using the international criteria proposed by the revised Response Evaluation Criteria in Solid Tumors (RECIST) Committee (version 1.1) and immune-related response criteria (irRC). Any evaluable or measurable disease must be documented at screening and reassessed at each subsequent tumor evaluation. If a patient is found to have disease progression by RECIST, at the discretion of the treating physician, the patient may remain on study. Baseline evaluation of disease status by CT or MRI required within 28 days prior to first dose of avelumab. The first scheduled re-scan should be performed and evaluated 7 to 8 weeks after Cycle 1, Day 1 treatment, with subsequent scheduled scans intended every 8 to 9 weeks thereafter. If progression is confirmed by irRC, the patient should typically be removed from study (i.e. in the absence of therapeutic benefit and an alternative agreement and arrangement specified by protocol). If irRC show the patient to not have disease progression, the patient may remain on study.

Evaluable for toxicity: All patients will be evaluable for toxicity from time of their first treatment with avelumab.

Evaluable for objective response: Only those patients who have measurable disease present at baseline, have received at least one cycle of therapy, and have had their disease re-evaluated will be considered evaluable for response. These patients will have their response classified according to the definitions stated below. (Note: Patients who exhibit objective disease progression prior to the end of cycle 1 will also be considered evaluable.)

If a patient discontinues study treatment for reasons clearly not related to study treatment, after completing fewer than one planned infusion of avelumab, and/or receiving <75% of the total intended dose of avelumab over the first cycle of treatment + an additional 14 days (i.e. first 28 days after initiating patient's first dose of avelumab), then that patient will be considered not evaluable for response to study treatment and may be replaced with a new patient.

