5.5. Number of Patients and Replacement of Patients Who Discontinue Early

Approximately 25 patients evaluable for response are anticipated to enroll in this study at Vanderbilt University Medical Center.

In general, it is intended that patients will be treated until disease progression or intolerable toxicity. The criteria for patient discontinuation are listed in Sections 9 and 11.

If a patient discontinues study treatment for reasons clearly not related to study treatment, after completing fewer than one planned infusion of avelumab, and/or receiving <75% of the total intended dose of avelumab over the first cycle of treatment + an additional 14 days (i.e. first 28 days after initiating patient's first dose of avelumab), then that patient will be considered not evaluable for response to study treatment and may be replaced with a new patient.

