11. ADVERSE EVENT MANAGEMENT

11.1. Criteria for Holding Treatment for Adverse Event Possibly Related to Avelumab

No dose *reductions* of avelumab are permitted for the management of adverse events experienced by individual patients in this study.

As outlined below, *treatment delays* of up to 4 weeks (28 days) from last dose of avelumab are allowed.

Avelumab Treatment Should be DELAYED up to 4 Weeks (28 days) for the following Adverse Events if at least Possibly related to Avelumab:

- Any Grade \geq 3 drug-related adverse event, with the exception of alopecia and the following laboratory exceptions for lymphopenia, leukopenia, AST, ALT, and total bilirubin:
 - Grade 3 lymphopenia or leukopenia do not require a dose delay.
 - If subject had baseline AST, ALT, or total bilirubin within normal limits, then delay dosing for drug-related Grade \geq 2 liver function toxicity.
 - If subject had baseline AST, ALT, or total bilirubin that was Grade 1, then delay dosing for drug-related Grade \geq 3 liver function toxicity.
- Any AE, laboratory abnormality, or intercurrent illness regardless of severity or attribution to avelumab which, in the judgment of the investigator, warrants delaying investigational treatment with avelumab.

IMPORTANT:

The above list does NOT include other events which may require holding study treatment – even in cases of severity less than Grade 3 and regardless of attribution to study drug. Events such as Immune-Related Adverse Events (irAEs) of Special Interest, Infusion Reactions, Hypersensitivity, or Tumor Lysis Syndrome (if applicable) should be managed according to local institutional practice.

Dose delay criteria apply for drug-related adverse events – i.e. events which in the investigator's opinion are possibly, probably, or definitely related to avelumab. For adverse events deemed unlikely or unrelated to avelumab (e.g. related to disease), the medical judgement of the investigator should determine the extent to which a treatment delay is appropriate.

If avelumab treatment is delayed for > 4 weeks (28 days) from the last dose of avelumab, the subject must be permanently discontinued from study therapy, except as may be specified in Sections 9.4 and 11.3.

The window for a maximal 4 week (28 day) avelumab treatment delay begins on the calendar day of the most recent avelumab treatment preceding an event in question, and concludes on the calendar day that an immediately subsequent avelumab treatment is initiated.

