17. STATISTICAL CONSIDERATIONS

17.1. Study Design / Endpoints

The primary objective of this clinical trial is to estimate the objective response rate (ORR) from the best response a patient experiences prior to progression (using RECIST v1.1 and irRC). Twenty-five patients will be enrolled on this clinical trial. This regimen will be considered sufficiently active to

warrant further study in more definitive trials if 4 patients experience an objective response among 25 treated.

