17.4. Reporting and Exclusions

All patients included in the study must be assessed for safety, tolerability, and response to treatment, even if there are major protocol treatment deviations or if they are ineligible. Each patient will be assigned one of the following response categories: 1) complete response, 2) partial response, 3) stable disease, 4) progressive disease, 5) early death from malignant disease, 6) early death from toxicity, 7) early death because of other cause, or 9) unknown (not assessable, insufficient data).

All patients meeting the eligibility criteria and received study drug for 2 weeks should be included in the main analysis of the clinical benefit rate. Patients in above response categories 4-9 should be considered to have a treatment failure (disease progression). Thus, an incorrect treatment schedule or drug administration should not result in exclusion from the analysis of the response and clinical benefit rate.

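### Section 13.1 drops treated patients without a re-scan from the response denominator; Section 17.4 leans the other way, and the plan does not fix the population for the primary ORR

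*Combined protocol and SAP*

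**What the plan says.** Section 13.1 restricts evaluability for objective response to patients with measurable baseline disease who "have received at least one cycle of therapy, and have had their disease re-evaluated will be considered evaluable for response". It makes one allowance: "Patients who exhibit objective disease progression prior to the end of cycle 1 will also be considered evaluable". The first scheduled re-scan is 7 to 8 weeks after the first dose (7.1 note 6; 13.1).

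Section 5.5, repeated in 13.1, adds a separate rule. It covers a patient who discontinues for reasons clearly unrelated to treatment, with less than one infusion and/or under 75% of the intended dose in the first 28 days; "then that patient will be considered not evaluable for response to study treatment and may be replaced with a new patient".

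Section 17.4 gives every included patient a response category. The list includes "5) early death from malignant disease, 6) early death from toxicity, 7) early death because of other cause" and an unknown/not assessable class, and "Patients in above response categories 4-9 should be considered to have a treatment failure (disease progression"). Its analysis set, however, is eligible patients who "received study drug for 2 weeks should be included in the main analysis of the clinical benefit rate". That rate is neither an objective in Section 3 nor the endpoint in 17.1.

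Section 17.1 states the go rule as met "if 4 patients experience an objective response among 25 treated"; 17.3 words it as 4 or more of 25 treated. Sections 5.5 and 17.2 describe the 25 as evaluable for response.

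**The concern.** Take a patient who receives two doses and dies of the cancer in week 5 without a scan. Under 13.1 this patient is outside the response denominator. Under the 17.4 categories the same patient is a failure inside it. Sections 17.1 and 17.3 refer to neither section, so two analysts following the text could report different primary ORRs from the same data.

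The difference has a direction. A patient never re-scanned cannot have a documented response, so leaving such patients out can only raise the ORR. The patients lost this way are likely to be those who do worst earliest. ORR is a primary objective and carries a formal test and a go decision, so its denominator should be fixed before results are seen.

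**Working it through.** **Inputs.** From 17.3: exact one-sample binomial test, one-sided 5%, null ORR 5%, alternative 21%, n = 25, go at 4 or more responses. From 4.1: median overall survival of 13 months on chemotherapy and 4 months on best supportive care. From 4.5: 8.9 and 4.6 months on avelumab in PD-L1 positive and negative NSCLC. The documents give no rate of treated patients without a re-scan; that rate is an assumption throughout.

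**1. The plan's own figure.** P(X ≥ 4 | 25, 0.05) = 0.0341 and P(X ≥ 4 | 25, 0.21) = 0.801. With a cut-off of 3 the type I error would be 0.127. The stated 80% power and the 4-response rule reproduce.

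**2. The replacement arithmetic.** Two doses are intended in the first 28 days (Days 1 and 15). A stop before the second gives 1/2 = 50%, below 75%. So an early stop meets the dose condition, and replacement then turns on whether the reason is called clearly unrelated.

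**3. Same data, two denominators.** With 4 responses and enough patients treated to reach 25 evaluable:

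| Unscanned | Treated | ORR, 13.1 set | ORR, all treated (Wilson 95%) |
|---|---|---|---|
| 0 | 25 | 4/25 = 16.0% | 16.0% (Table 3: 6.4–34.6%) |
| 3 | 28 | 16.0% | 4/28 = 14.3% (5.7–31.5%) |
| 4 | 29 | 16.0% | 4/29 = 13.8% (5.5–30.6%) |

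If instead exactly 25 are treated and 3 are unscanned and not replaced, the 13.1 set gives 4/22 = 18.2% against 4/25 = 16.0%.

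**4. Type I error of the 4-response rule on all treated.** P(X ≥ 4 | n, 0.05):

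| n treated | 25 | 26 | 27 | 28 | 29 | 30 |
|---|---|---|---|---|---|---|
| alpha | 0.0341 | 0.0387 | 0.0437 | 0.0491 | 0.0548 | 0.0608 |

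The rule holds 5% up to 28 treated and exceeds it from 29.

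**5. The same question by unscanned share.** Let u be the share of treated patients without a re-scan, none of them responders, and let the true ORR among all treated be 5%. The ORR in the evaluable set is then 0.05/(1 − u), and the chance of a false go is P(X ≥ 4 | 25, 0.05/(1 − u)):

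| u | 0 | 8% | 12% | 15% | 22% |
|---|---|---|---|---|---|
| false go | 0.034 | 0.044 | 0.051 | 0.056 | 0.073 |

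It equals 0.05 when the evaluable ORR is 0.05656, so u = 1 − 0.05/0.05656 = 0.116.

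**6. How large might u be?** As a rough proxy, take deaths by Day 49 to Day 56 under exponential survival, 1 − 2^(−days/(30.44 × median in months)). A 13-month median gives 8.2–9.3%, 8.9 months gives 11.8–13.3%, 4.6 months gives 21.5–24.2% and 4 months gives 24.3–27.3%. At the 13-month figure, which is for this disease on chemotherapy, the false-go chance is 0.044–0.046.

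**The case against.** The strongest reply is that the go rule does name its denominator. Sections 17.1 and 17.3 both say treated, and so does the sentence introducing Table 3. A reader might infer from the clash with 13.1 that the plan gives no denominator at all; the text does not support that. It leans to all treated. What stands is that 5.5 and 17.2 aim for 25 evaluable patients and some early stops may be replaced, so once more than 25 are treated the phrase no longer identifies a set.

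Three other strong readings go too far:

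- *Section 5.5 removes every unscanned patient.* It has no re-scan condition and covers only clearly unrelated stops with too little dose. The broader removal comes from 13.1.
- *Section 17.4 counts all of them as failures for ORR.* Its main set requires eligibility and two weeks of drug, so a death before two weeks may fall outside that set as well. Its closing sentence does name response, but only to prevent exclusion for schedule or administration errors.
- *Section 11.1 makes a cancer death an unrelated reason for replacement.* Its wording, "For adverse events deemed unlikely or unrelated to avelumab (e.g. related to disease"), concerns attribution of adverse events for dose delays. Nothing carries it into 5.5. It shows only that 5.5 leaves the term open.

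The unscanned group may also be small. A scan is due at end of treatment unless done in the previous 28 days (7.5), within 28 days of the last dose for stops without progression (8.3), and every 8–9 weeks thereafter until progression (7.1 note 19). That leaves mainly early deaths and patients too ill to scan. The calculation in step 5 also assumes that the 5% null describes all treated patients; if it describes evaluable patients, the false-go chance stays at 0.034.

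**Conclusion.** The conflict is in the operative text, and no sentence ranks the two rules. Applying 13.1 as written can only raise the ORR relative to all treated: by 1.7 points with 3 unscanned of 28 treated (16.0% against 14.3%) and by 2.2 points with 4 of 29 (16.0% against 13.8%). If every treated patient is re-scanned, the re-scan condition has no effect.

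A reader might infer that the trial's 5% error rate is broken. The documents do not support that. It needs an unscanned share of about 12% or more, which the documents do not give, and the medians that would produce such a share come from NSCLC or best supportive care. The go decision is affected only when there are exactly 4 responses and at least 29 patients treated. The firm part of the finding is the undefined primary population and the one-sided bias in the ORR; the error-rate effect is conditional and small. The point should be corrected because the remedy is cheap and has to be in place before the data are seen.

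**What to change.** 1. In 17.1 and 17.3, state that the primary ORR and the go rule use all patients who received any avelumab; that patients without a post-baseline assessment, including replaced patients, count as non-responders; and that ORR in the 13.1 evaluable set is supportive.
2. In 17.4, name ORR in the failure rule.
3. In 5.5 and 13.1, state that death from the cancer, or its worsening, is not an unrelated reason for replacement.
4. If more than 28 patients are treated, report the exact type I error of the 4-response rule for that number (0.0548 at 29).

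The cost is a few sentences in an amendment, one extra analysis line and a slightly lower reported ORR. No scans, visits or patients are added.

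Raising the cut-off to 5 responses from 29 treated is optional. It would bring the type I error at 29 down to 0.0136, but power at an ORR of 21% would be 0.759, below the planned 80%. If the 21% refers to the 25 evaluable patients, power would be P(X ≥ 5 | 25, 0.21) = 0.627. Reporting the exact error rate is enough for a pilot.
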